4 STUDY DESIGN

4.1 General Description

This study is a multi-center, randomized, open-label clinical trial evaluating the efficacy and safety of ESG as an adjunct to life-style intervention for weight loss and improvement in obesity-related co-morbidities compared to lifestyle intervention alone in participants with a BMI ≥ 30 and ≤ 40 kg/m² who have failed to achieve and maintain weight loss with a non-surgical program.

Participants will be recruited from outpatient clinical weight loss clinics and from study-related institutional review board (IRB) approved advertisements. The cohort will include nor more than 50 patients without at least one of a) hypertension (HTN) on one or more anti-hypertensive medications or b) type II diabetes mellitus (DM) on oral agents only with HbA1c ≤ 9 . Enrollment will be tracked continuously and enrollment closed to non-DM, non-HTN patients after meeting the target for that group.

Two hundred eligible participants will be stratified into three groups (obesity, obesity-hypertension, and obesity-diabetes) and then block-randomized 1 to 1.5 to treatment (80 participants) and control (120 participants) groups alone as depicted in the diagram on page 16. All treatment group participants will undergo endoscopy and those without endoscopic contraindications will undergo the ESG. All control subjects will follow a low-calorie, healthy lifestyle intervention only for 12 months. After 12 months of lifestyle intervention, eligible control participants will crossover to receive the ESG. Those who had the ESG will undergo a repeat upper endoscopy at 52 weeks +- 4 weeks to evaluate the durability of the plications and re-tighten the ESG if needed with continued follow-up for 12 additional months.

The study will have two levels:

1. Level 1: the randomized study phase with primary outcomes for both groups evaluated at 12 months
2. Level 2: the crossover, non-randomized study phase with outcomes for a) the initial treatment group at 24 months post ESG (12 months after the re-tightening procedure) b) for the controlled cross-over group evaluated at 12 months after ESG

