4.2 Endpoints

4.2.1 Effectiveness

Primary:

- % EWL at 12 months from randomization by randomized arm measured at the week 52 visit. The null hypothesis is no difference in mean %EWL between randomized arms.

Secondary:

- Proportion with $\geq 25\%$ EWL at 12 months by randomized arm
- Change in hypertension in the ESG group compared to LS only

- Proportion of patients off or with reduction in their antihypertensive medications in the randomized control arm compared to lifestyle control at 12 months
- Change in systolic and diastolic blood pressure in the randomized arm compared to lifestyle control at 12 months
- Comparing diastolic and systolic blood pressures as continuous variables 12 months after ESG (compared to baseline) in the entire cohort that received ESG both in the randomized and cross-over segments of the trial
- Change in type II diabetes in the ESG groups compared to LS only
 - Proportion of patients off or with reduction in their diabetes medications in the randomized arm compared to lifestyle control at 12 months
 - Change in HgbA1c in the randomized arm compared to lifestyle control at 12 months
 - Comparing HgbA1c as a continues variable 12 months after ESG (compared to before) in the entire cohort that received ESG both in the randomized and cross-over segments of the trial.
- %TBWL in the ESG group compared to LS only
- % of patients in the ESG group achieving > 5% TBWL compared to LS only
- % of patients in the ESG group achieving > 10% TBWL compared to LS only
- Durability of the plication evaluated by endoscopy at 12 months (level 1) and effectiveness of re-tightening procedure performed at 12 months (level 1) in maintaining and / or enhancing weight loss at 24 months. Durability of the plication and procedure is defined as greater than 70% of the cohort undergoing repeat endoscopy achieving a score of ≥ 1 out of 3 prior to re-tightening (Grading system and evaluation in appendix). Efficacy of re-tightening is defined as $\geq 50\%$ of the cohort undergoing the re-tightening maintaining or losing weight compared to the re-tightening weight at 12 months after the re-tightening procedure.
- Incidence of esophagitis at repeat endoscopy at 12 months (level 1). (LA grading system in form in appendix)
- Changes in quality of life assessed using standard validated questionnaires (IWQOL-lite and SF-36)
- Changes in depression assessed using PHQ-9 questionnaire

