ESG patients will undergo a standard moderate intensity life-style intervention administered over 12 visits in the first year after ESG. Participants will be required to follow up with their prescribing physician to make any necessary changes to their hypertension and/or type II diabetes medications at 3, 6, 9 and 12 months. Completion of patient follow-up with providers for medication adjustment will be captured with completion of the appropriate CRF at the corresponding visits. In the event that participants are unable to contact their physician or participants are experiencing symptoms related to the medication dosing requiring urgent action, the study team will make any necessary

changes in their medication dosing and document these changes appropriately in the relevant CRFs. Any medication changes will be monitored and recorded by the study team.

All ESG patients in Level 1 (80) will be evaluated for %EWL at the end of Level 1 (measurement of primary endpoint). Those ESG patients who have achieved >25% EWL at the end of Level 1 will not undergo a repeat endoscopy and will continue to follow-up with a lifestyle intervention in Level 2. Those ESG patients who have not achieved >25% EWL at the end of Level 1 will undergo a repeat upper endoscopy at 52 to 60 weeks to assess the durability of the plications (see Plication Durability form), and perform a retightening of the ESG if needed. The need for re-tightening will be determined by the PI after evaluating the sutures based on a grading system presented in the retightening CRF. The retightening procedure will be performed if at least one of the three portions (proximal, mid, and distal) of the endoscopic sleeve is non-tubular in shape. For each tubular third of the sleeve, 1 point will be given. A score of 3/3 means the entire (proximal, mid, and distal) sleeve is tubular in shape. A score of 2/3 means that one-third of the sleeve is no longer tubular. A score of 1/3 means that two-thirds of the sleeve are no longer tubular. Finally a score of 0/3 means the entire sleeve is no longer tubular. Re-tightening will occur for patients with a score of 0, 1 or 2.

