TABLE 2. MERIT SCHEDULE OF EVENTS (Year 2, Level 2, Treatment Group, 80 Patients)							
	ESG retightening [†]	Post-Op Clinical Eval ^{**}	Follow-up after ESG retightening OR Week 60 [†]	Week 72-76*	Weeks 80, 88, 96	Week 104 (Final Year 2 visit)	Unscheduled Visit
Visit Number	17	-	18	19	20, 21, 22	23	
Informed consent							
Complete Physical Exam (CPE) by Investigator or Investigator delegated / medically qualified team member				X		X	X
Investigator or Investigator delegated/medically qualified team member exam			X	X	X	X	X
EKG if (> 50 yo)							
Formal nutritional assessment							
Formal psychology evaluation							
Pregnancy test (females of childbearing potential only)							
Laboratory tests ^{**}				X		X	
Questionnaires [#]				X		X	
Inclusion/exclusion criteria							
Endoscopy / Procedure	X						
Procedure Assessment Form	X						
GERD Questionnaire + Activity Assessment Form			X	X	X	X	
Weight, BMI/height, Waist and Hip Circumference Form	X		X	X	X	X	X
Vital Signs Form	X		X	X	X	X	X
Adverse Events Form		X	X	X	X	X	X
Medications Form ^{##}			X	X	X	X	X
Post-enrollment Nutrition / Exercise / satiety counseling and assessment			X	X	X	X	
Subject Satisfaction Questionnaire (study termination)						X	

** Electrolytes, Creatinine, CBC, Iron, TIBC, B12, 25-hydroxy Vitamin D, TSH, HgA1c, fasting blood sugar and insulin, PTT, fasting lipids profile (total cholesterol, LDL, HDL, and Triglyceride), ALT, AST, ALK-P, total bilirubin, direct bilirubin, BUN, total protein, albumin, CRP, urinalysis; also include PYY-1, GLP-1 and total Ghrelin pending sites' availability to analyze

IWFQOL-Lite, SF36, PHQ9, Pittsburg Sleep Quality Index (PSQI), Three factor eating questionnaire (TFEQ)

Record all medications including dose and frequency; especially diabetes and blood pressure medication.

++ Post-op phone call, no clinic visit, to occur between 18-36 hours post-op

+ ESG retightening to occur between Weeks 52-60 for those who qualify with in-clinic follow-up visit to occur 4 weeks post retightening, or subjects to continue to Week 60 for those who do not qualify for ESG retightening

*Lab draw to occur between Week 72-76

5.6.1.1.3 Schedule of Events for Control Group, Crossover in Year 1, Level 1

TABLE 3. MERIT SCHEDULE OF EVENTS (Year 1, Level 1, Control Group, 120 patients)									

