7 STATISTICAL ANALYSIS

7.1 Power and Sample Size

The primary endpoint for power and sample size is %EWL at 12 months. The null hypothesis is no difference in mean %EWL between ESG and LS randomized arms ($H_0: \mu_t = \mu_c$ where μ_t is the average %EWL in the ESG group and μ_c is average %EWL in the LS group). We will perform a two-sided hypothesis test at alpha level 0.05 (alternative hypothesis $H_a: \mu_t \neq \mu_c$) Based on the published literature with the ESG technique a conservative presumption is 25% EWL in the ESG arm with a standard deviation (SD) of 30% at 12 months compared to 10% EWL on LS alone with SD of 5%. We plan a 1:1.5 randomization scheme that allocates 3 patients to LS for every 2 to ESG at the time of randomization. Based on a two-sample t-test with unequal variances and two-sided alpha=0.05, we would have 80% power to detect a difference of 15% in average %EWL between groups with 34 patients allocated to ESG and 51 randomized to LS. 90% power would require group sizes of 45 and 68, respectively. To allow for dropout, and more importantly, to power exploratory aims for obesity comorbidity subgroups, we propose the initial randomization of 200 patients – 80 to ESG and 120 to LS.

120 subjects are initially randomized to LS in level 1. Of these, we anticipate up to 20% will achieve a successful decrease of $\geq 25\%$ in %EWL through LS alone at 12 months. Further, we anticipate up to 20% may be lost to follow up or drop out prior to 12 month follow up. Thus, we anticipate at least 77 ($120 * 0.8 * 0.8$) subjects to continue to level 2 and be offered ESG. We will test the one-sample hypothesis (non-randomized) that of those offered ESG at 12 months, average change in %EWL will be at least 10%. Based on a one-sample t-test with two-sided alpha=0.05 and standard deviation at 24 months of 30%, 70 subjects completing ESG would have 98% power to detect an effect of 25% reduction in %EWL.

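### If the Treatment Group section governs, the plication-durability verdict on the procedure comes only from ESG patients not above 25% EWL; sections 4.1 and 5.5.1.1.2 conflict on this and must be reconciled

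*Combined protocol and SAP*

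**What the plan says.** Section 4.2.1 (Effectiveness) lists plication durability among the secondary endpoints and attaches a success rule: "Durability of the plication and procedure is defined as greater than 70% of the cohort undergoing repeat endoscopy", each "achieving a score of ≥ 1 out of 3 prior to re-tightening".

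Two places say who has that endoscopy, and they differ:

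- Section 4.1 (General Description) sets no weight-loss condition: "Those who had the ESG will undergo a repeat upper endoscopy at 52 weeks +- 4 weeks".
- Section 5.5.1.1.2 (Treatment Group) makes it depend on the 12-month weight result: "Those ESG patients who have achieved >25% EWL at the end of Level 1 will not undergo a repeat endoscopy". The others, those "who have not achieved >25% EWL at the end of Level 1 will undergo a repeat upper endoscopy at 52 to 60 weeks", are examined and graded.

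The schedules in section 5.6 fit the second version. Table 1 has no endoscopy at week 52. Table 2 has one only in the re-tightening column, and its footnote tells the remaining patients what to do: "or subjects to continue to Week 60 for those who do not qualify for ESG retightening". That footnote does not itself repeat the 25% EWL condition.

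Section 7.2.2 uses the endoscopic score in a regression on later weight change and labels that comparison observational. Section 7.3 (Missing Data) does not mention ESG patients who have no endoscopic score.

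**The concern.** Under section 5.5.1.1.2, entry to the durability denominator is decided by 12-month %EWL, which is the trial's primary outcome. The success rule is nevertheless worded as a verdict on the plication and the procedure, and a reader would take it to describe the ESG arm.

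If sleeve shape and weight loss are related, the share scored as durable in this subgroup need not match the share in the arm, and the pass/fail result could differ from the one the whole arm would give. The scored group also shrinks as ESG performs better, so a more successful treatment leaves less evidence on whether its sleeves last.

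**Working it through.** **Inputs.** From section 7.1: 80 ESG patients, mean 25% EWL and SD 30% at 12 months. From section 5.5.1.1.2: no repeat endoscopy above 25% EWL. From section 4.2.1: pass if more than 70% of those re-scoped score at least 1.

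**The plan's own figure.** The documents give no number for how many ESG patients will be re-scoped. The nearest stated figure using the same mean and SD is the sample size in section 7.1. A Welch t-test (difference 15, SDs 30 and 5, two-sided alpha 0.05) gives 80.1% power at 34/51 and 90.2% at 45/68, so both stated sizes reproduce.

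**Step 1: how many are unscored.** The planned mean equals the cut. P(%EWL > 25) = 1 − Φ((25 − 25)/30) = 0.50, and 0.50 × 80 = 40. At this mean the result holds for any SD if the distribution is symmetric. Other means are assumptions, taken with SD 30 and a normal distribution:

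| Assumed ESG mean %EWL | P(above 25%) | Unscored of 80 |
|---|---|---|
| 20 | 0.434 | 34.7 |
| 25 (plan) | 0.500 | 40.0 |
| 30 | 0.566 | 45.3 |
| 40 | 0.691 | 55.3 |

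Section 7.1 describes its value as cautious ("a conservative presumption is 25% EWL in the ESG arm with a standard deviation (SD) of 30% at 12 months"), so the upper part of the table is at least as relevant as the lower. Dropout is ignored here.

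**Step 2: what a pass says about the arm.** With 40 scored, 70% is 28 patients, so the smallest pass is 29/40 = 72.5%. Whole-arm limits:

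- all 40 unscored counted as non-durable: 29/80 = 36.25%
- all 40 unscored counted as durable: (29 + 40)/80 = 86.25%

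These are extremes and need no assumption about direction.

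**Step 3: what a gap would do (illustration).** Assume a true whole-arm value of 80%, half the arm scored, and patients above 25% EWL scoring at least 1 more often by g points. The scored group's true value is then 80 − g/2. The exact binomial probability of 29 or more out of 40 is:

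| Gap g (assumed) | True value in scored group | P(pass), n = 40 |
|---|---|---|
| 0 | 80% | 91.2% |
| 10 | 75% | 71.5% |
| 20 | 70% | 44.1% |
| 30 | 65% | 20.5% |

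The like-for-like reference is 91.2%. With all 80 scored (57 or more needed) the figure is 97.8%, but the drop from 97.8% to 91.2% is due to the smaller number scored, not to selection.

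**The case against.** **Section 4.1 would score everyone.** If it governs, every ESG patient who attends is graded and the selection problem disappears. This stands: the documented error is the conflict, and everything computed above is conditional on section 5.5.1.1.2. The detailed procedure and the schedules favour that reading but do not settle it.

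**The denominator is stated.** A reader might infer that the endpoint cannot be computed, or that the plan leaves the unscored patients undefined. It does neither: section 4.2.1 restricts the rule to those re-scoped, so the others are excluded. What remains is that the claim is wider than the denominator.

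**The direction is unproven.** It is tempting to say that the rule understates durability because intact sleeves should go with greater weight loss. No figure in the documents links sleeve score to 12-month %EWL, and the gaps in step 3 are assumptions.

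**The score cut.** A reader might also infer a contradiction, because sleeves scoring 1 or 2 count as durable while "Re-tightening will occur for patients with a score of 0, 1 or 2". An endpoint cut and a treatment trigger may legitimately differ. Nor do the documents say how many scored sleeves would be re-tightened: with 70% scoring at least 1, the share scoring 0 to 2 could be 30% (all the others score 3) or as much as 100% (none scores 3). Only a reporting suggestion survives.

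**Consequence.** This is one descriptive, single-arm secondary endpoint. It affects neither the primary %EWL comparison nor the safety threshold. This stands and limits the weight of the point.

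**Conclusion.** The point holds conditionally. Sections 4.1 and 5.5.1.1.2 disagree on who has the repeat endoscopy. If the latter stands, the durability verdict applies to ESG patients not above 25% EWL and cannot be read as a verdict on the procedure.

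At the plan's mean, and assuming symmetry, about half the arm is unscored, and a bare pass leaves the whole-arm share anywhere between 36% and 86%. That range rests only on 40 of 80 being unscored. The fall in pass probability from 91.2% to between 71.5% and 20.5% rests in addition on an assumed arm value of 80% and assumed gaps of 10 to 30 points. It shows how sensitive the rule could be and is not evidence of bias in either direction. The point is worth correcting before analysis because it changes what may be concluded about durability, but its reach is confined to this endpoint.

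**What to change.** 1. Reconcile sections 4.1 and 5.5.1.1.2, and check the schedules in section 5.6 against the result. Which endoscopy rule applies is for the sponsor.
2. If section 5.5.1.1.2 stands, restate the section 4.2.1 endpoint as durability among ESG patients with 25% EWL or less at 12 months, and remove the claim about the procedure as a whole.
3. Beside it, report the number of ESG patients unscored, and the whole-arm share with unscored patients counted first as all durable and then as all non-durable.
4. Optionally, show the full score distribution, including the share at 3 of 3, next to the share at 1 or more.

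The cost is a change of endpoint wording and a few table lines. Items 2 to 4 add no patient, visit or procedure. The drawback is a narrower durability claim.

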7.2.2 Secondary Aims

Continuous secondary outcomes, including change in systolic and diastolic blood pressure and change in HbA1c, QOL questionnaires such as the SF-36, PHQ-9, and eating behavior scores will be compared between treatment arms using ANCOVA with adjustment for the same variables specified in the primary analysis.

Binary outcomes, including proportion with $\geq 25\%$ reduction in %EWL and incidence of esophagitis will be compared between treatment arms by Pearson Chi-square test.

Among patients randomized to the treatment ESG group, the association between the durability of plication at repeat endoscopy (score ≥ 1 on EGD grading system) and number of sutures required for re-tightening with change in EWL from 12 months to 24 months will be assessed using linear regression with adjustment for BMI, %EWL between randomization and 12 month follow up, HTN status, and DM status. This is an observational comparison.

Among patients randomized to the control LS arm, the percent EWL from the 12 month assessment to the 24 month assessment will be measured. This percentage will be compared to percent EWL in the same group with lifestyle intervention only in the first 12 months using a one sample t-test.

Among all subjects, %EWL will be compared at 24 months between initial and delayed ESG. However, this is not considered a comparison of randomized arms as follow up is not continued for patients with $\geq 25\%$ EWL from LS at 12 months.

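### The durability endpoint can be met while most, or even all, examined sleeves meet the protocol's own criterion for re-tightening

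*Combined protocol and SAP*

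**What the plan says.** Section 4.2.1 lists durability of the plication among the secondary effectiveness endpoints and gives it a pass/fail rule for the whole cohort: "greater than 70% of the cohort undergoing repeat endoscopy achieving a score of ≥ 1 out of 3 prior to re-tightening". Section 7.2.2 applies the same cut to individual patients, as a predictor of weight change from 12 to 24 months: "durability of plication at repeat endoscopy (score ≥ 1 on EGD grading system".

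Section 4.2.1 points to an appendix for the grading system, but section 5.5.1.1.2 sets it out in full. "For each tubular third of the sleeve, 1 point will be given", so the range is 0 to 3. "A score of 1/3 means that two-thirds of the sleeve are no longer tubular". The consequence of the score follows: "Re-tightening will occur for patients with a score of 0, 1 or 2". Only 3/3 is spared.

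The two sections that define who is examined differ. Section 4.1: "Those who had the ESG will undergo a repeat upper endoscopy at 52 weeks +- 4 weeks". Section 5.5.1.1.2: "Those ESG patients who have not achieved >25% EWL at the end of Level 1 will undergo a repeat upper endoscopy", with a window of 52 to 60 weeks.

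The documents give no reason for cutting at 1, no expected distribution of scores, and no test or confidence interval for the 70% rule.

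**The concern.** The same score, from the same endoscopy, is read in two ways. Under the endpoint rule, only a sleeve that has opened in all three thirds counts against durability. Under the treatment procedures, a sleeve that has opened in any third qualifies for further suturing, and the description of that procedure calls the open portions non-restrictive. A sleeve scoring 1 or 2 is thus a durability success and a re-tightening case at once.

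At stake is what the trial can say about whether the plication lasts. A report could state that durability was shown next to a high re-tightening rate in the same patients, and a reader who saw only the first statement would be misled. The denominator adds to this. If only patients with poorer weight loss are examined, the figure describes them and not everyone who received ESG.

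**Working it through.** The plan states no sample size, power, null rate or expected result for this rule, so there is no figure of its own to reproduce. The overlap follows from the text alone. The probabilities are illustrations under stated assumptions.

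**Step 1. Overlap, from the text.**

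| Score | Tubular thirds | Counts as durable (4.2.1, 7.2.2) | Meets re-tightening criterion (5.5.1.1.2) |
|---|---|---|---|
| 0 | 0 | no | yes |
| 1 | 1 | yes | yes |
| 2 | 2 | yes | yes |
| 3 | 3 | yes | no |

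If every sleeve scores 1, the share scoring at least 1 is 100%, the rule is met, and the share meeting the re-tightening criterion is also 100%.

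**Step 2. Number examined.**
- Under section 4.1, all who had ESG: up to 80 in the randomized ESG arm ("All ESG patients in Level 1 (80) will be evaluated for %EWL").
- Under section 5.5.1.1.2, only those not above 25% EWL. Section 7.1 assumes a mean of 25% and an SD of 30%. If %EWL is roughly normal, half fall at or below 25%: 80 × 0.5 = 40.
- With 20% dropout: 40 × 0.8 = 32. Section 7.1 states that rate for the lifestyle arm; applying it to ESG is an assumption.

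More than 70% means at least 23 of 32, 29 of 40 or 57 of 80.

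**Step 3. Score model (assumed).** Let p be the probability that a third is still tubular. With independent thirds, P(score ≥ 1) = 1 − (1 − p)³ and P(meets re-tightening criterion) = 1 − p³. For p = 0.5, both equal 1 − 0.125 = 0.875. For p = 0.4, they are 1 − 0.216 = 0.784 and 1 − 0.064 = 0.936. Correlation between thirds of one sleeve is represented by a beta-binomial with intraclass correlation (ICC). The rule is met when X ≥ r, where X is binomial with n and P(score ≥ 1), and r is the minimum count from Step 2.

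| p | ICC | P(score ≥ 1) | Meets re-tightening criterion | Rule met, n = 32 | n = 40 | n = 80 |
|---|---|---|---|---|---|---|
| 0.5 | 0 | 0.875 | 87.5% | 0.996 | 0.997 | >0.999 |
| 0.4 | 0 | 0.784 | 93.6% | 0.87 | 0.86 | 0.95 |
| 0.3 | 0 | 0.657 | 97.3% | 0.30 | 0.23 | 0.18 |
| 0.5 | 0.2 | 0.800 | 80.0% | 0.91 | 0.91 | 0.98 |
| 0.5 | 0.4 | 0.725 | 72.5% | 0.62 | 0.58 | 0.65 |
| 0.5 | 0.6 | 0.650 | 65.0% | 0.27 | 0.21 | 0.15 |

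At the other extreme, if sleeves hold or fail as a whole and half score 0, the rule is met with probability 0.003 at n = 40.

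**Step 4. Precision.** The rule is applied to the observed percentage. The smallest passing counts have exact 95% confidence intervals of 0.53 to 0.86 (23/32), 0.56 to 0.85 (29/40) and 0.60 to 0.81 (57/80), so a bare pass is compatible with a true share well below 70%.

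**Step 5. What if the 70% bar were moved to 3/3?** With independent thirds, P(3/3) = p³. At p = 0.5 and p = 0.7 (0.125 and 0.343) the bar is met with probability below 0.0001 at all three sizes. At p = 0.9 (0.729) it is met with probability 0.64, 0.60 and 0.68 at n = 32, 40 and 80.

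**The case against.** The two cuts may serve different purposes. The endpoint may ask whether any plication persists, while the treatment rule is a sensitive trigger for touching up any open part. The protocol never calls a score of 1 or 2 a failure. It expects re-tightening to be a shortened procedure confined to the open portions, and section 4.2.1 speaks of enhancing weight loss as well as maintaining it. The cut is openly pre-specified, belongs to one of many secondary endpoints, and has no bearing on the primary comparison.

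Part of this stands. A low bar can be a legitimate choice, and the 0 to 3 score is recorded, so the information is not lost. But the documents do not state that purpose, and the word attached to the low bar is durability.

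A reader might infer that the rule would declare durability almost surely. The documents do not support that. The outcome depends only on the share scoring 0, which they do not give. Independent thirds is a favourable assumption for that reading, because the three thirds belong to one sleeve made in one session. Examining only patients with poorer weight loss could also lower the scores, though this too is undocumented.

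A reader might also infer that 3/3 with the same 70% threshold is the right replacement. Nothing in the documents justifies that threshold for 3/3, and Step 5 shows that it would almost never be met unless nearly all segments held.

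**Conclusion.** The concern holds as an inconsistency between an endpoint label and the protocol's own grading. Durability can be declared while most, or even all, examined sleeves meet the re-tightening criterion. That statement rests on sections 4.2.1 and 5.5.1.1.2 alone.

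Its likely frequency is uncertain. With half of the segments tubular, the probability that the rule is met runs from above 0.99 (independent thirds) through about 0.6 (ICC 0.4) to 0.2 to 0.3 (ICC 0.6) for 32 to 40 patients, while 65% to 87.5% of sleeves meet the re-tightening criterion. These figures rest on assumed values of p, ICC and n. The primary endpoint is unaffected. The point should be corrected because the published durability statement could mislead and the remedy is cheap. No view is taken on which patients should be re-tightened.

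**What to change.** 1. In sections 4.2.1 and 7.2.2, relabel the criterion of more than 70% scoring at least 1, and the matching patient-level cut, as sleeve not completely lost instead of durability.
2. Report as the durability result the full distribution of scores 0, 1, 2 and 3, and the proportion scoring 3/3 (not meeting the re-tightening criterion), with exact 95% confidence intervals. Do not carry the 70% threshold over to 3/3 unless the sponsor justifies it.
3. Reconcile sections 4.2.1 and 5.5.1.1.2 on what the score means.
4. Reconcile sections 4.1 and 5.5.1.1.2 on which ESG patients have the repeat endoscopy, and in what window, since this sets the denominator. If only those not above 25% EWL are examined, state that the durability figure applies to that subgroup.

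The cost is endpoint and analysis wording. The score is already captured on the re-tightening form, so no new data are needed. The downside for the sponsor is a less favourable durability figure.

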2.2 Clinical Data to Date

The feasibility of ESG was first demonstrated in humans in the US in 2013.²⁰ Since then, the technique has gained wide clinical adoption in the US and world-wide with more than 2000 cases performed. Multiple single-arm prospective and retrospective studies have demonstrated the safety and minimally invasive nature of the technique and reported %TBWL of about 18% at 12 months.^{21, 22} Furthermore, studies have demonstrated physiologic perturbations resulting from creation of the ESG and its association with increased satiation and metabolic effects that are potentially important to control the metabolic dysregulation associated with obesity.²³ In a recent multicenter study of 248 patients enrolled at Mayo Clinic, Cornell Medical Center, and Madrid Hospital, ESG was associated with 18% and 20% TBWL at 12 and 18 months, respectively²³. More importantly, in this large series, incidence of serious adverse events (SAE) was only 2% and none of these SAEs required any surgical intervention. No mortality was reported.

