3 STUDY OBJECTIVES

1. Assess if ESG achieves safety and efficacy threshold as defined by joint societal consensus statement by ASGE and ASMBS
2. Assess the impact of ESG on obesity related co-morbidities (Hypertension and Diabetes)
3. Assess the mid-term durability of weight loss achieved by ESG at 24 months.
4. Assess the impact of re-tightening the ESG on weight loss trajectory.

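### The 50% rule for calling re-tightening effective has no comparator, untreated rate or confidence bound, so its false-positive rate is undefined and meeting it cannot answer objective 4

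*Combined protocol and SAP*

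**What the plan says.** Objective 4 in section 3 is to "Assess the impact of re-tightening the ESG on weight loss trajectory". The matching secondary endpoint in section 4.2.1 is a decision rule. Re-tightening counts as efficacious with at least 50% "of the cohort undergoing the re-tightening maintaining or losing weight compared to the re-tightening weight at 12 months after the re-tightening procedure", that is, weighing no more 12 months later than at re-tightening.

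The cohort is set in section 5.5.1.1.2: "Those ESG patients who have not achieved >25% EWL at the end of Level 1 will undergo a repeat upper endoscopy", and then "Re-tightening will occur for patients with a score of 0, 1 or 2". The same section has re-tightened patients repeat the transitional diet and has all patients continue a lifestyle programme in year 2, with 6 visits instead of 12.

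Section 7 gives this rule no hypothesis, untreated rate, interval, test or sample size. The only related analysis, in section 7.2.2, regresses the change in EWL from 12 to 24 months on plication durability and number of re-tightening sutures. The plan itself calls that comparison observational. It has no term for re-tightened versus not re-tightened, and none for before versus after.

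**The concern.** The rule uses one fact per patient: whether weight a year later is at or below the weight at re-tightening. It then compares the observed share with 50%, with no allowance for sampling error. Two things are missing.

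- **A reference.** Some patients would hold or lose weight without re-tightening. Unless that share is known or estimated, a result of 50%, 60% or 70% cannot be read as an effect.
- **Precision.** The cohort will be a fraction of the ESG arm, so the observed share will be imprecise.

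At stake is the conclusion on a named objective. A repeat procedure could be reported as efficacious on data that are compatible with no effect. The rule also ignores the weight course before re-tightening, so it does not measure a change in trajectory.

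**Working it through.** **The plan's own figures.** There is none to reproduce for this rule. Section 7.1 gives power for other comparisons only. Its primary calculation does reproduce: 34 and 51 patients give 80.1% power against the stated 80%.

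**Cohort size (assumption).** Section 7.1 plans "80 to ESG and 120 to LS" and assumes "25% EWL in the ESG arm with a standard deviation (SD) of 30% at 12 months compared to 10% EWL on LS alone". If EWL is normal with mean 25%, half the ESG arm is at or below 25%: 80 × 0.5 = 40. Applying to the ESG arm the dropout of up to 20% that the plan states for the lifestyle (LS) arm gives 64 × 0.5 = 32. Patients with a score of 3 are then removed. I use n = 20 to 40.

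**Chance that the rule is met.** Let p be the share who would hold or lose weight with no effect of re-tightening. The documents do not give p. With X ~ Binomial(n, p), the rule is met with probability P(X ≥ ⌈n/2⌉).

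At p = 0.50:

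| n | Needed | Probability |
|---|---|---|
| 20 | 10 | 0.588 |
| 30 | 15 | 0.572 |
| 40 | 20 | 0.563 |
| any odd n | (n+1)/2 | 0.500 |

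For other values of p:

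| p | n = 20 | n = 30 | n = 40 |
|---|---|---|---|
| 0.30 | 0.048 | 0.017 | 0.006 |
| 0.40 | 0.245 | 0.175 | 0.130 |
| 0.45 | 0.409 | 0.355 | 0.316 |
| 0.55 | 0.751 | 0.769 | 0.787 |
| 0.60 | 0.872 | 0.903 | 0.926 |
| 0.70 | 0.983 | 0.994 | 0.998 |

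**Precision at the threshold.** The exact (Clopper-Pearson) 95% CI for 15/30 is 31% to 69%.

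**With a confidence bound.** The smallest counts whose exact two-sided 95% lower limit exceeds 50% are below, with the chance of reaching them at several true shares.

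| Cut-off | True share 50% | 60% | 70% | 80% |
|---|---|---|---|---|
| 15/20 | 0.021 | 0.126 | 0.416 | 0.804 |
| 21/30 | 0.021 | 0.176 | 0.589 | 0.939 |
| 27/40 | 0.019 | 0.211 | 0.703 | 0.981 |

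The bound holds error near 2% only against a share of 50%. If the untreated share were 60%, 21/30 would still be reached 17.6% of the time with no effect. The bound therefore deals with sampling error and does not deal with attribution.

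**The case against.** The strongest reply is that p is unknown and may be low. Those re-tightened have not exceeded 25% EWL, have at least one non-tubular third of the sleeve, and have fewer lifestyle visits in year 2. If such patients usually regain, having half of them hold or lose weight is a real hurdle: with 40 patients and p = 0.40 the rule is met 13% of the time.

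Other facts point the other way. Patients selected on a low week-52 result will tend to look better later by regression to the mean, the transitional diet is repeated, and lifestyle support continues. Section 2.2 also reports that "ESG was associated with 18% and 20% TBWL at 12 and 18 months, respectively", but that series was not selected for poor response and the figures stop at month 18. The documents do not settle the direction. This part of the reply stands: no single false-positive rate can be claimed.

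It is also fair that this is part of one secondary endpoint with no alpha attached, in a phase that section 4.1 labels non-randomized, and that section 7.2.2 adds a regression. The regression softens the gap. It does not close it, because it contrasts plication scores and suture counts and not re-tightening itself.

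A reader might infer that the rule is a coin-flip whenever re-tightening does nothing. The documents do not support that, because it requires an untreated share of exactly 50%.

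**Conclusion.** The concern holds in a limited form. The 50% rule has no comparator, untreated rate or confidence bound, and nothing in section 7 provides one. Its false-positive rate is undefined. It is 50% to 59% for n = 20 to 40 if the untreated share is 50%, and at n = 30 it runs from about 2% to 99% as that share goes from 30% to 70%. Both the cohort size and the untreated share are assumptions. The lack of a reference and the width of the interval at 15/30 do not depend on the untreated share.

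Meeting the rule would show at most that about half of the re-tightened patients held or lost weight. It would not show an impact of re-tightening on trajectory. The primary comparison and the safety endpoints are unaffected.

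**What to change.** 1. **Section 4.2.1.** Report the proportion with its exact two-sided 95% CI, and count the criterion as met only if the lower limit exceeds 50% (15/20, 21/30 or 27/40).
2. **Same place.** State that meeting it shows only that most re-tightened patients held or lost weight. It does not attribute this to re-tightening, because the cohort is uncontrolled, is selected on a low week-52 result and repeats the transitional diet.
3. **Section 7.2.2.** Add a descriptive weight trajectory before and after re-tightening, from weights already scheduled in section 5.6. Label it observational. Warn that selection at week 52 makes the earlier course look worse and the later one better with no effect of treatment. Show ESG patients not re-tightened for context only, since most of them will be those above 25% EWL.
4. **Sections 4.1 and 5.5.1.1.2.** Reconcile them. The first gives repeat endoscopy to those who had the ESG, at 52 weeks plus or minus 4. The second gives it only to those not above 25% EWL, at 52 to 60 weeks. This sets the denominator.

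The cost is wording and one descriptive analysis, with no new visits or patients. The downside is a harder criterion: with 30 patients it is met 59% of the time at a true share of 70%, and 94% at 80%.
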